3.4 Subject Selection

Two subject populations will be studied: smokers (n=10) and non-smokers (n=70). The pilot study will recruit up to 10 people (non-smokers) and the main study will recruit 70 people (10 smokers & 60 nonsmokers).

3.4.1 Inclusion Criteria – both smokers and non-smokers.

Healthy men and women (n= up to 80) between the ages of 18 and 40 will be recruited for the study. Subjects who participate in the pilot study will also be eligible to participate in the main study.

Subjects must have been fully vaccinated for COVID-19 – people are considered fully vaccinated for COVID-19 ≥ 2 weeks after they have received the second dose in a 2-dose series (e.g., Pfizer-BioNTech or Moderna), or ≥ 2 weeks after they have received a single-dose vaccine (e.g., Johnson and Johnson).

Additional Inclusion Criteria for Smokers: currently smoking at least one cigarette each day.

3.4.2 Exclusion Criteria

- Cardiovascular disease

- Respiratory disease
- Recent (within 4 weeks) respiratory or COVID-19 symptoms
- Diabetes
- Pregnancy
- HIV Infection
- Orthopedic or rheumatologic conditions which would interfere with cycle use
- Inability to produce a sputum plug
- Daily use of antioxidant supplements, excluding those in a multivitamin. These supplements include Vitamin C or E, selenium, beta-carotene, lycopene, lutein, zeaxanthin and ginkgo biloba. Supplements taken less frequently but at least once a week will be reviewed by the principal investigator for eligibility determination.

Additional Exclusion Criteria for Non-smokers: history of smoking within the past 5 years.

4. Study Variables

4.1 Independent Variables or Interventions

The independent variable is the ozone exposure. The exposure will take place in the Controlled Exposure Facility at EOHSI. The CEF consists of three major components: 1) the exposure chamber; 2) the air pollutant generation system; and 3) the control systems. The CEF is a large stainless steel room (7.3 ft. high x 13.5 ft. wide x 9 ft. deep; volume= 887 cubic feet) in which the air flow, temperature and humidity can be varied and well controlled. A divider separates the chamber into two compartments, so that two subjects can be exposed simultaneously. There is a lavatory in the chamber for extended exposure studies. For the clean air exposure, ambient air that supplies the exposure chamber will be treated using a series of processes, which include cooling/heating, humidification/dehumidification, and filtration through a carbon filter, a KMnO₄ purifier, and HEPA filters. The clean air enters the CEF through two diffusers located in the ceiling and exits through the perforated stainless steel floor without recirculation.

For ozone exposure sessions, ozone will be generated in situ by an ozone arc-generator (Ozone Research & Equipment Corporation, Phoenix, AZ), mixed with the filtered clean air and will enter the CEF through the two air diffusers. The ozone concentration will be achieved by adjusting the ozone output and the air mixing flow through the chamber. Based on previous studies [43], ozone can be precisely controlled during an exposure session. The ozone concentration will be monitored in real time using an API Model 450 ozone analyzer (API, Inc., San Diego, CA). The sensitivity of the instrument is 1 ppb, and response time is less than 20 sec. Noise is less than 0.7 ppb.

Additionally, during each exposure session, additional air pollutants will be monitored. CO concentration will be measured using a real-time Langan T15 CO gas monitor. NO/NO₂ concentration will be monitored by a TEI Model 42C TL Trace Level NO-NO₂-NOx real-time Analyzer (Thermo Electron Corporation, Franklin, MA). PM_{2.5} mass concentration will be measured using a real-time personal PM monitor (SidePak, TSI Inc., MN).

4.2 Dependent Variables or Outcome Measures

Induced sputum samples will be collected at the Environmental and Occupational Health Sciences clinic. The relative concentrations of M1 and M2 macrophages in the induced sputum sample will be assessed in the Rutgers University Flow Cytometry/Cell Sorting and Confocal Microscopy Core facility (<http://www.flowcyt.rutgers.edu/>). Cells will be separated from mucus plugs, stained with fluorescent antibodies and then analyzed by flow cytometry. Leukocytes will initially be separated from epithelial cells by light scatter and by CD45 expression, and macrophages identified by HLA-DR expression [44]. Flow cytometry will also be used to assess macrophage phagocytosis and oxidative burst. To confirm their phenotype, sputum macrophage subpopulations will be sorted and expression of inflammatory proteins and additional M1/M2 macrophage markers not detectable by flow cytometry will be analyzed by RT-PCR and immunocytochemistry.

Macrophage response may vary by genotype, specifically GST polymorphisms. The genotyping will be done by the Rutgers University Cell and DNA Repository (RUCDR) on a fee for service basis. De-identified samples will be sent to RUCDR. Any sample remaining after the genetic analyses will be destroyed.

Supernatant from the induced sputum sample, EBC, and urine will be analyzed for cytokines, chemokines, prostaglandins and novel eicosanoids. The analysis will first be done in samples from the pilot study to identify markers of interest for the main study. All analyses will be done at the Rutgers Flow Cytometry Lab and in [name] lab in EOHSI. Subjects will be asked for permission to store excess samples for future use by the study investigators.

Oral washes and oropharyngeal swabs as well as aliquots of induced sputum and EBC samples will be given to [name] for microbiome analysis.

Specimens (induced sputum, exhaled breath condensate, and blood samples) will be analyzed for oxidized and nitrosylated variants of surfactant protein D. All analyses will take place in the Rutgers Flow Cytometry Lab.

Data from the stress questionnaires, collected before and after the exposure and before the follow-up sputum induction, will be examined as possible modifiers of the response. Subject fitness, calculated by their heart rate recovery during the exposure visit, will also be examined as a possible modifier.

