The current USEPA standard for ozone is 0.070 ppm averaged over an 8 hour day. This is meant to protect not only healthy individuals, but those more sensitive to ozone's effects such as infants, children, those with asthma, and those with other chronic lung conditions such as COPD. The proposed exposure concentration of ozone (0.2 ppm, 3 hours) is almost twice maximal levels reported in the world's most polluted cities (i.e., Mexico City); however, this concentration and higher concentrations (up to 0.4 ppm, 2 hours) with exercise have been used extensively for mechanistic studies at United States Environmental Protection Agency (USEPA), the University of Southern California (USC), the University of California, San Francisco (UCSF), the University of California, Davis (UC Davis), the University of Rochester, and other institutions for over 40 years with no adverse effects in hundreds of subjects, including asthmatics, beyond transient and expected physiologic declines in spirometry, reported [26-34]. For instance, one recent study at University of Rochester exposed healthy exercising subjects to 0.2 ppm of ozone for 3 hour, identical to our proposed protocol [27]. 7-10% declines in FEV1 were observed 0.5 hours after exposure had largely resolved by 4 hours following exposure. Another study using the roughly equivalent 0.3 ppm ozone for 2 hours with exercise showed transient FEV1 declines of 7-15% [26]. Our exposures will be limited to 3 hours and will only occur once. Based on published studies, subjects are not expected to experience more than transitory effects including symptoms of mucosal irritation, cough or headache, but these are expected to be mild and dissipate within an hour after the exposure is terminated.

3. Research Design and Methods

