current or recent respiratory symptoms. If subjects report any symptoms within the previous 4 weeks, the visit will be rescheduled. Subjects will be asked to refrain from eating for 2 hours prior to the exposure visit. At the start of the visit, the subject's blood pressure, pulse, and temperature will be measured. IOS and spirometry will be performed before and after the exposure session. Two questionnaires will also be administered before the exposure session: a stress questionnaire and a symptom questionnaire. If the subject reports the presence of any respiratory symptoms, the exposure session will be canceled. During the exposure, heart rate will be measured using a wireless monitor (H7; Polar USA). Subjects will be asked to alternate (every 15 minutes) rest and mild/moderate exercise periods on a cycle ergometer to maintain an average heart rate of approximately 60% maximum heart rate (220-age). The exercise is necessary as healthy human subjects are relatively insensitive to ozone [39, 40]. The exercise schedule may be modified to maintain the ventilation rate or for the subject's comfort. After the exposure session, the stress and symptom questionnaires will be administered. An exposure type questionnaire will also be administered immediately after the exposure. If the subject reports any physical symptoms or has a 20% decrease in his/her FEV1 after the exposure session, the study physician will be consulted. Subjects will be given verbal and written instructions to contact the Robert Wood Johnson Medical School Pulmonary Division if they experience any breathing problems after leaving EOHSI. Subjects will inform the responding pulmonologist that he/she is a study subject. As an additional precaution, subjects will be given a rescue inhaler to use only if directed to do so by the responding pulmonologist. Subjects will be shown how to use the inhaler prior to leaving the EOHSI clinic. The pulmonologist will inform [name] of any calls made to the pulmonologist and any treatment. The symptom questionnaire will be administered to each subject the day after exposure. For subjects returning at 24 hours for the post-exposure sputum sample, the questionnaire will be administered in person. For all other subjects the questionnaire will be administered by phone. As a secondary check, the questionnaire will ask the study subject if he/she contacted the Pulmonary Division. If the subject reports the presence of any symptoms or called the Pulmonary Division, the study physician will be consulted, prior to the collection of any samples.

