
Immediately before and after each exposure session EBC samples will be collected using the same methods as in the screening visits. In addition to the EBC samples, urine, oral washes, oropharyngeal swabs, and blood samples will be collected before and after each exposure session. During the second exposure visits, an additional blood sample will be collected for genotyping of GST polymorphisms. The urine samples will be analyzed for eicosanoids and other markers of inflammation. The blood samples will be processed by either [name] lab (research blood for future use) or the Rutgers University Cell and DNA Repository facility core at EOHSI (sample for genetic analysis).

Subjects will be asked to return for a follow-up visit either 1, 2, or 3 days after each exposure visit. Subjects will be asked to refrain from eating for 2 hours prior to the visit. The blood pressure, pulse rate, and oral temperature will be checked. IOS and spirometry will be performed and an induced sputum sample will be collected. The symptom and stress questionnaire will be administered. The blood, urine, oral washes, oropharyngeal swabs, and EBC samples will also be collected.

Sputum samples obtained after the ozone exposure may be compared with samples collected either at the screening visit or after the clean air exposure. If the subject is randomized to ozone exposure first and is unable to produce a sputum sample after the ozone exposure, the subject will be withdrawn from the study.

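### Protocol Section 4.2 allows stress scores taken after exposure, and heart-rate recovery from an unspecified session, as effect modifiers, so an apparent modifier can arise where there is none

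*Protocol*

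**What the plan says.** Protocol Section 4.2 names two sets of candidate modifiers besides GST genotype. Stress scores, "collected before and after the exposure and before the follow-up sputum induction, will be examined as possible modifiers of the response", form the first. The second is fitness: "Subject fitness, calculated by their heart rate recovery during the exposure visit, will also be examined as a possible modifier".

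Section 3 (Research Design and Methods) confirms the timing of the stress scores:

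- Before each session: "Two questionnaires will also be administered before the exposure session: a stress questionnaire and a symptom questionnaire".
- After each session: "After the exposure session, the stress and symptom questionnaires will be administered".
- At the follow-up visit one, two or three days later, when the outcome sputum is induced: "The symptom and stress questionnaire will be administered".

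For heart rate, Section 3 says: "During the exposure, heart rate will be measured using a wireless monitor". Each subject has two exposure visits, one with ozone and one with clean air, in random order. Section 4.2 refers to the exposure visit in the singular and does not say which.

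No passage limits the modifier analysis to pre-exposure values or gives the later stress scores another role. Neither Protocol Section 7 nor the SAP contains a modifier term.

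**The concern.** An effect modifier should be fixed before the exposure whose effect it is said to modify. Two of the three stress scores per session come after the exposure, and the last is taken at the visit that supplies the macrophage outcome. If post-ozone stress is associated with the macrophage response, the data cannot separate three explanations: stressed subjects respond more, strong responders feel worse, or something else in that session moved both.

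The documents make such a link plausible without showing it. Section 2 expects "transitory effects including symptoms of mucosal irritation, cough or headache" after ozone and cites FEV1 declines of 7-10% in a study with the same exposure. Section 3 also lets the exercise schedule be changed for comfort, so discomfort under ozone could alter the workload from which heart-rate recovery is calculated.

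At stake is a statement about who is susceptible to ozone. More subjects would not cure the problem: if the shared cause exists, the false-modifier rate rises with sample size.

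**Working it through.** **Inputs from the documents.** Protocol Section 3.3 gives 16 subjects per group, the 0.05 level and an intra-person correlation of 0.5. I take 16 as one collection-time group, since 3 x 16 = 48 matches the 48 non-smokers in Section 3, and I take tests as two-sided.

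**The plan's own figure.** The 16 cannot be strictly reproduced, because the sample size behind the 8% SE is not given. Reading the SE as 8% of 1.6 (0.128) and assuming 15 source subjects, the SD of change is 0.128 x sqrt(15) = 0.496, and a two-group t-test at 90% power needs 16 per group. The point does not depend on this; 16 only sets n below.

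**Assumed input.** The documents give no correlation between stress change and macrophage response. I use 0.5 and show 0.3 and 0.7.

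**Test.** The correlation between the candidate modifier and D, the within-subject ozone-minus-clean-air difference. In every model pre-exposure stress is unrelated to D.

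**Three models, and the correlation r that each implies between post-ozone stress and D when the assumed correlation is 0.5:**

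1. *Direct link.* Post-ozone stress = 0.7 x pre + 0.714 x reaction, and the reaction correlates 0.5 with D. r = 0.714 x 0.5 = 0.357.
2. *Shared session noise.* The ozone effect is the same for everyone (1.18 SD). Outcomes have variance 1 and intra-person correlation 0.5, so D has variance 1. Post-ozone stress = pre + change, with variance 2, and the change correlates 0.5 with the ozone-session noise (SD sqrt(0.5)). r = 0.5 x sqrt(0.5) / sqrt(2) = 0.25.
3. *Latent susceptibility.* A hidden trait adds variation of SD 0.5 to the ozone effect and correlates 0.5 with the stress change. D has variance 1 + 0.25 = 1.25. r = 0.5 x 0.5 / (sqrt(2) x sqrt(1.25)) = 0.158.

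**Approximate rejection rate.** P(Z > 1.96 - m) + P(Z < -1.96 - m), with m = atanh(r) x sqrt(n - 3).

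| Model | r | m, n=16 | Rate, n=16 | m, n=48 | Rate, n=48 |
|---|---|---|---|---|---|
| 1 | 0.357 | 1.35 | 27% | 2.51 | 71% |
| 2 | 0.25 | 0.92 | 15% | 1.71 | 40% |
| 3 | 0.158 | 0.57 | 9% | 1.07 | 19% |

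**Simulated rates** (20,000 trials per cell for model 1, 40,000 for models 2 and 3):

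| Assumed correlation | n=16, models 1 / 2 / 3 | n=48, models 1 / 2 / 3 |
|---|---|---|
| 0.3 | 13% / 8% / 6% | 31% / 17% / 10% |
| 0.5 | 27% / 15% / 9% | 72% / 41% / 19% |
| 0.7 | 53% / 27% / 13% | 96% / 70% / 33% |

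Pre-exposure stress is declared a modifier in about 5% of trials throughout. In model 3, so is a value from the clean-air session (simulated without carry-over).

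**Two limits.** In model 2, a uniform shift of stress by ozone (0, 0.5 or 1 SD) made no difference, and with zero correlation the rate was about 5%. A shift alone does no harm; the post-ozone value must share a cause or noise with the response. In models 1 and 3 the ozone response may truly vary between people. The error there is to credit that variation to stress, which is only a fellow result.

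**The case against.** The strongest reply is that the mechanism is assumed. No passage says that ozone alters stress scores or heart-rate recovery. The symptoms expected are mild and should clear within about an hour, while the follow-up stress score is taken 24 to 72 hours later. Subjects are blinded, which limits stress from knowing the exposure. Section 4.4 cites chamber work in smokers that found no added risk of acute deterioration in heart rate or symptoms. This stands as a limit on certainty, though the smoker data concern harm and do not address stress scores or recovery.

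A reader might infer that fitness is taken from the ozone session. The text does not say so. The fair criticism is that the session is unspecified; a clean-air value would be largely safe. The simulations model stress and give no separate figure for an ozone effect on recovery.

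A reader might also take 27% or 72% as the size of the problem. Those come from the model with the most direct link. At the same assumed correlation the other two give 15% and 9% at n=16. The n=48 column requires pooling the three time groups, whereas Protocol Section 7 and the SAP analyse by time-point.

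Finally, the modifier work is exploratory, has no stated model or decision rule, and already includes a sound candidate in pre-exposure stress. That is correct and confines the consequence.

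**Conclusion.** The point holds in limited form. Section 4.2 puts post-exposure and follow-up stress on the same footing as pre-exposure stress and leaves the heart-rate session open. Followed as written, it can yield a false modifier. With an assumed correlation of 0.5, the rate is about 9-27% at n=16, against about 5% for pre-exposure values. Over assumed correlations from 0.3 to 0.7 it runs from 6% to 53%, and at zero there is no inflation.

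Two stronger readings are not supported. It would be too much to say that any modifier conclusion must be wrong: even the assumed inputs make a false modifier possible, not certain. Nor does the problem reach the primary analysis, because the SAP's three paired t-tests on the M2 to M1 ratio contain no modifier.

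**What to change.** In Protocol Section 4.2:

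- Limit the modifier analysis to the stress score before the first exposure, GST genotype, and heart-rate recovery from the clean-air session, not the ozone session.
- For heart-rate recovery, include session order in the model, or add a sensitivity analysis in subjects who had clean air first. Order is randomised and no washout interval is stated, so clean-air recovery follows ozone in subjects given ozone first and cannot be called untouched by it.
- Analyse post-exposure and follow-up stress as outcomes, ozone versus clean air.
- Label the modifier analyses exploratory.

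No new data are needed, since the protocol already collects all of these. The SAP is written in the past tense; if the modifier analyses have been run, the same rule can govern how they are labelled and reported.

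The cost is that post-exposure stress is no longer tested as a modifier. The sensitivity analysis also uses fewer subjects: about 16 / 2 = 8 per time group if the order is balanced, which the documents do not state.

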4.4 Risks of Harm

Ozone exposure: The proposed exposure concentration of ozone (0.2 ppm, 3 hours) is almost twice maximal levels reported in the world's most polluted cities (i.e., Mexico City); however, this concentration and higher concentrations (up to 0.4 ppm, 2 hours) with exercise have been used extensively for mechanistic studies at EPA, USC, and other institutions for over 40 years with no adverse effects, beyond transient physiologic declines in spirometry, reported. Our exposures will be limited to 3 hours and will only occur once. Based on published studies, subjects are not expected to experience more than transitory effects including symptoms of mucosal irritation, cough or headache, but these are expected to be mild and dissipate within an hour after the exposure is terminated. Based on prior experiments looking at monitored

chamber exposures of smokers to ozone, it appears there is no increased risk of acute deterioration in pulmonary function, respiratory pattern, heart rate or symptomatology, even at ozone doses >3 times the concentration proposed in this protocol [45]. Thus, there does not appear to be an increased risk of harm by exposing smokers to ozone as described in this protocol. Prior to the exposure, subjects will complete a symptom questionnaire. If subjects report the presence of any symptoms, the exposure session will be canceled. During the exposure sessions, the participants are continually observed through a window to assure that they are not exhibiting any visual signs of physical problems and wear a sensor for continuous monitoring of heart rate. A physician with a code cart is on-call during the entire procedure to respond to any subject complaints or situations. If a subject develops any symptoms of chest pain, dizziness, or other symptoms/signs of concern to the subject or the study technician, the physician will speak with and examine the subject and decide if the exposure session may continue. The covering physician will examine the subject, including EKG if indicated, and make an appropriate triage decision, including referral via ambulance to the emergency department. Regardless of the physician's recommendation, the study subject may choose to end the session at any time. At the end of each exposure session, the subject will complete a symptom questionnaire. This questionnaire will be reviewed by the study technician and a physician to ensure that the subject is ready to resume daily activities. The subject will also be asked to complete the symptom questionnaire the next day (by phone or in person). If the subject reports any symptoms, he/she will be referred to the study physician. All subjects will be asked to return for their scheduled follow-up visit.

As a precaution against delayed bronchospasm after an exposure session, after-hours response has been arranged with the pulmonary division Robert Wood Johnson Medical School. After each exposure session, subjects will be given written and verbal instructions to call the pulmonary division for any delayed respiratory problems. A physician will be available 24 hours a day/7 days per week. Subjects will also be provided a rescue inhaler to be used only if advised by the responding pulmonologist. Prior to leaving EOHSI, subjects will be instructed in the use of the inhaler and asked to return the inhaler at their follow-up visit. At each follow-up visit, the meter on the inhaler will be checked for use. Any use will be reported to the study physician to determine if the subject can continue with the study. The inhaler will be discarded once the subject has completed the study.

The study has a single ozone exposure and a single clean air exposure. If the subject experiences bronchospasm either during or after the ozone exposure, the subject will be asked to return for his/her scheduled follow up visit for the sputum collection. Since no further ozone exposure will occur, the subject will be permitted to continue with the study and participate in the clean air exposure, if not done previously. In the unlikely event that the subject experiences bronchospasm either during or after the clean air exposure and has not yet had the ozone exposure, the subject will be considered ineligible and his/her participation will stop. If the ozone exposure session has been completed, the subject will be asked to continue in the study and return for a follow-up visit.

Sputum induction: Sputum induction with hypertonic saline may cause reversible bronchoconstriction in some individuals. Bronchoconstriction has been observed primarily in asthmatic subjects who have pre-existing bronchial hyperreactivity. In order to reduce the risk

of bronchoconstriction, potential subjects who have a history of asthma, a history of symptoms consistent with bronchial hyperreactivity, or abnormal spirograms will be excluded from participation in the study. The sputum induction will be done only during clinic hours in EOHSI, when a physician is available. As a further precaution against bronchospasm, all subjects will be pretreated with albuterol 180 mcg or 2 puffs of a standard metered inhaler prior to the start of induction. Post-albuterol spirometry will be done to determine a baseline FEV-1 during induction. Our induction protocol consists of 3 segments of inhalation of nebulized saline at increasing concentrations. After each of the 3 segments spirometry is done. If the FEV-1 decreases from the baseline by more than 20% after a segment, the procedure will be stopped. An additional 180mcg of albuterol will be administered and spirometry will be repeated 15 minutes afterward. If the FEV-1 has recovered ($\geq 80\%$ baseline FEV-1) the subject will be permitted to leave EOHSI. If the FEV-1 is still depressed ($< 80\%$ baseline FEV-1), the subject will be referred to care at the EOHSI clinic and the referral will be documented as an adverse event. At any point during the induction, if the subject complains of any breathing difficulties, the induction will be stopped and the subject will be referred to care at the EOHSI clinic. The episode will be reported as an adverse event.

Albuterol: Albuterol, a short-acting bronchodilator, will be administered before induction via a rescue inhaler to prevent bronchoconstriction and possibly afterward to treat difficulty breathing, wheezing or shortness of breath due to bronchoconstriction. Temporary side effects from albuterol include tremor, palpitations, and headache. These effects may last four to six hours.

Genotyping: The selected assays currently have no immediate application to the diagnosis or treatment of any disease, but may relate to the inflammatory response. The primary risk from the testing is the loss of confidentiality. Every effort will be made to keep the results confidential.

Venipuncture: Slight pain, some bleeding, or bruising may occur when blood is drawn for the routine laboratory tests.

Oropharyngeal Swabs: The swabbing will be performed by a clinic nurse or medical assistant to reduce the possibility of a gag reflex.

Oral wash: No physical risk but subjects may experience a salty taste.

IOS: Subjects may experience brief, temporary lightheadedness during the IOS measurement.

